Finally, IRRs have been hypothesized to be a reaction by autoantibodies to the treatment drug or possibly from the release of cytokines from CD20 expressing cells as they are destroyed by ocrelizumab causing a “cytokine storm”. Understanding this process may lead to mechanisms that may aid in ameliorating these infusion reactions. If they are associated with ADA, then it might be possible to predictively premedicate these patients only. Alternatively, if they are associated with cytokine release, it may be possible to eliminate premedication in patients who are already CD20⁺ cell depleted in subsequent infusions. Therefore, we will assay the profile of certain cytokines in the serum 4 hours after start of ocrelizumab infusion.

Since ocrelizumab has entered the market, third party payers within and outside the US have required that the FDA or EMA approved versions of anti-CD20 monoclonal antibodies be used in the treatment of MS, namely ocrelizumab. Currently, we estimate several thousand MS patients in the US and Sweden are taking rituximab currently. Thus, it will be important to demonstrate that switching from a chimeric anti-CD20 to a more fully humanized anti-CD20 does not lead to unexpected infusion reactions and does not increase the probability of development of anti-drug antibodies.

The Rocky Mountain MS Center (RMMSC) at the University of Colorado Anschutz Medical Campus prescribed rituximab infusions for 533 MS patients in the last 12 months, of which 323 patients received their infusion at the University of Colorado Hospital's Outpatient Infusion Center between September, 2015-March, 2016. The RMMSC is one of the few sites nationwide with large numbers of MS patients treated with rituximab. On March 28, 2017, Ocrevus (ocrelizumab) was approved by the FDA for the treatment of primary progressive and relapsing multiple sclerosis. With the approval of ocrelizumab, current rituximab users are being counselled by their MS providers at RMMSC to consider switching to ocrelizumab if it is the only anti-CD20 MAB covered by their insurance.

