2.2 Secondary Objectives

Secondary Objective: Our secondary objective is to assess the impact of switching from rituximab to ocrelizumab (**only in the switching group**) on the incidence and prevalence of anti-drug antibodies to ocrelizumab. The presence of anti-drug binding antibodies will be assessed prior to the first and third ocrelizumab infusion and six to twelve months after the last ocrelizumab infusion. The serum drawn before the first infusion of ocrelizumab will be the baseline comparator since these patients will only have been exposed to at least two rituximab infusions over 6 months with no prior exposure to ocrelizumab. This means we will have 100 serum samples prior to ocrelizumab exposure and 200 after ocrelizumab exposure. These assays will be performed by PPD Bio A

Laboratories (in Richmond, VA) who will assess the anti-drug antibodies to ocrelizumab”, and “QPS (Netherlands) who will assess the anti-drug antibodies to rituximab as a single batch once all samples have been collected and cryopreserved.

Other secondary objectives that will be assessed in **the switching group** only include the following:

- a. We will assess the percent of ocrelizumab treated patients that exhibit early recovery of CD19+ and/or CD20+B cells (>1%) prior to each ocrelizumab infusion and at month 12 or 18 which is 12 or 18 months following the first infusion of ocrelizumab. We will compare this to the percent of patients with evidence of early recovery from rituximab as assessed by the baseline B cell panel. Our test will also identify CD19 antigen expression to confirm depletion since presence of anti-CD 20 MAB in patients blood may confound the CD-20 expression assay.
- b. We will assess cytokines to evaluate for possible contribution of a cytokine storm to infusion reactions. Cytokines will be assessed using the MesoScale platform. These blood samples will be collected before the start of each ocrelizumab infusion and following infusion completion. Blood samples will also be collected during a moderate or serious IRR.
- c. We will describe all adverse events and serious adverse events in addition to IRRs (for example infections) as described in the investigator’s brochure.

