3.3 Outcome Measures

3.3.1. Primary Outcome Measure

Primary endpoint:

- a. Primary endpoint: The primary end point will be proportion of infusions with ≥ 1 IRR between the switching and comparator groups.
- b. Secondary IRR assessments:
 - a. We will also report the difference in the total number of IRRs after each infusion of ocrelizumab in the switching group compared to similar rituximab infusions in the comparator group.
 - b. The difference in proportion of patients with ≥ 1 IRR across any of their infusions between the switching and comparator groups
 - c. We will also compare the proportion of patients with an IRR following day 1 infusion versus the proportion of patients with an IRR at day 15 and month 6 infusions of ocrelizumab in the switching group.
 - d. The severity of IRRs will be assessed following each infusion of ocrelizumab in the switching and comparator group using the National Cancer Institute's Common Terminology for Adverse Events Scale.⁶ The frequency of each severity grade of IRR will be compared in a similar fashion.

Nursing staff at the University of Colorado's Outpatient Infusion Center will be responsible for classifying the severity of an IRR for each patient at the end of every ocrelizumab and rituximab infusion using the scale below. Nursing staff will be asked to record the highest grade of an IRR that they observed or intervened upon for each patient after completion of their infusion.

Severity of IRR:

Grade 0: No infusion reaction

Grade 1: Mild reaction (transient flushing or rash drug fever < 38 degrees C); infusion interruption not indicated; intervention not indicated

Grade 2: Requires therapy or infusion interruption but responds promptly to symptomatic treatment (e.g., antihistamines, NSAIDs, narcotics); prophylactic medications indicated for 24 hours.

Grade 3: Prolonged (i.e., not rapidly responsive to symptomatic medication and/or brief interruption of infusion); recurrence of symptoms following initial improvement; hospitalization indicated for other clinical sequelae (e.g., renal impairment, pulmonary infiltrates)

Grade 4: Life threatening consequences; urgent intervention indicated.

Grade 5: Death

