3.3.2 Secondary Outcome Measures

- a. Anti-drug antibodies (ADAs): We will measure the number of patients who have treatment induced ADAs against rituximab and ocrelizumab prior to every ocrelizumab infusion (T_0 , T_1 , T_2) and at the research termination visit (T_3 =between month 12 and 18) in **ONLY** the switching group. This analysis will be performed by PPD Bio A Laboratories (in Richmond, VA) who will assess the anti-drug antibodies to ocrelizumab, and “QPS (Netherlands) who will assess the anti-drug antibodies to rituximab a single batch at end of study for the switching group.
- b. Treatment efficiency: We will measure B cell depletion before each ocrelizumab infusion (T_0 , T_1 and T_2), by the clinical laboratories (T cell and B cell panel) at the University of Colorado Hospital. We will measure the proportion of patients who are B cell depleted (CD-19+ and CD-20+) by the time of the next infusion and 6 to 12 months after the last infusion in the switching group.
- c. Cytokine profile: To better characterize infusion reactions and evaluate the contribution by either hypersensitivity reactions to ocrelizumab directly and/or by release of cytokines from dying CD20 positive cells, serum levels of cytokines will be evaluated. Cytokines will be measured using the MesoScale platform before the start of each ocrelizumab infusion, and after the infusion is completed (T_0, T_1, T_2, T_3). In addition, blood samples will be collected for those who experience a moderate to severe IRR to further examine cytokine profiles during an IRR. Plasma samples will be analyzed using the V-PLEX Human Biomarker 40-Plex Kit which assays for IFN- γ , IL-1 β , IL-2, IL-4, IL-6, IL-8, IL-10, IL-12p70, IL-13, TNF- α , GM-CSF, IL-5, IL-16, IL-7, IL-12/IL-23p40, IL-1 α , VEGF-A, IL-17A, IL-15, TNF- β , IL-8 (HA), MCP-1, MCP-4, Eotaxin, IP-10, MDC, Eotaxin-3, TARC, MIP-1 α , MIP-1 β , VEGF-C, VEGF-D, Tie-2, Flt-1/VEGFR-1, PIGF, FGF (basic), SAA, CRP, VCAM-1, ICAM-1 per manufacturer’s recommendation on a MesoScale SECTOR Imager 2400. This array of cytokines will provide information on the levels of cytokines being released during the infusion to determine if they are limited to those released by B cells. Patients will be categorized as either not having had an IRR (Grade 0), having had a mild

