Standard of care rituximab doses are 1000 mg given as first dose followed by 500mg (or 1000 mg if evidence of early B cell recovery) every 6 months thereafter. However, [The B cell depletion with rituximab can last up to two years in some patients with good efficacy demonstrated after a single dose in the HERMES study for up to a year.³](#) Patients are often out of window due to difficulties in obtaining insurance approval within the 6 month time window. Therefore, we will include those patients that receive rituximab infusions within a 12 month window.

Although ocrelizumab may be administered on an outpatient basis, patients may be hospitalized for observation at the discretion of the investigator. Ocrelizumab infusions should always be administered in a hospital or clinic environment under close supervision of the investigator or a medically qualified staff member. Each ocrelizumab infusion should be given as a slow IV infusion over approximately 150 minutes (2.5 hours) for the 300-mg dose. To reduce potential Infusion Related Reactions (IRRs), all patients will receive prophylactic treatment with 100 mg of methylprednisolone (or equivalent IV steroid), administered by slow IV infusion, to be completed approximately 30 minutes before the start of each ocrelizumab infusion.

It is also strongly recommended that the infusion is accompanied by prophylactic treatment with an analgesic/antipyretic such as acetaminophen/paracetamol (1 g) and/or an IV or oral antihistamine (such as IV diphenhydramine 50 mg or equivalent dose of alternative) 30 – 60 minutes prior to the start of an infusion to reduce potential IRRs. Patients administered a sedating antihistamine for the treatment or prevention of IRRs should be given appropriate warnings concerning drowsiness and potential impairment of ability to drive or operate machinery.

Since transient hypotension may occur during ocrelizumab infusion, the investigator may wish to withhold anti-hypertensive medications 12 hours prior to ocrelizumab infusion.

Ocrelizumab must not be administered as an IV push or bolus. Well-adjusted infusion pumps should be used to control the infusion rate, and ocrelizumab should be infused through a dedicated line. It is important not to use evacuated glass containers (to prepare the infusion), which require vented administration sets, because this causes foaming as air bubbles pass through the solution.

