monitored through standard of care assessments for this population to include a complete metabolic panel (CMP) and complete blood counts (CBC) with differential. Second, their immune profile will be evaluated through an immunoglobulin panel and analyzing T and B cell subsets using flow cytometry by the clinical laboratories at the University of Colorado Hospital. Samples for the cytokine analysis will be drawn on a similar schedule. For the cytokine analysis, blood samples will be collected prior to and after each infusion in CPT tubes. Because moderate to severe infusions reactions can delay infusions, we will plan to add an additional blood draw when these reactions are detected to keep timing of the blood draws more consistent and to capture any possible peak in cytokine levels during these reactions should they be occurring. Plasma will be derived by centrifuging at 1500g for 15 min and then will be aliquoted and stored at -80C. Cells will be reconstituted in freezing media (20% fetal bovine serum, 10% DMSO) and stored at -80C for further analysis. Additionally, plasma samples will be analyzed by MesoScale SECTOR Imager 2400 for evaluation of cytokine levels. Blood draws for the anti-drug antibody analysis will also be drawn at T₁ and sent to PPD Laboratories, Richmond, VA using cryopreserved blood samples as a single batch at the end of the study and analyzed for cytokine analysis.

Patients will receive 100 mg of methylprednisolone 30 minutes before administration of ocrelizumab at each infusion cycle (T₀-T₂). Following the infusion, nursing staff will record IRR using the National Cancer Institute's Common Terminology for Adverse Events Scale. Patient self-assessment of IRRs will also be captured. Adverse events will also be recorded as described in Section 5 by either the nursing staff or study coordinators. Finally, at the last research termination visit (T₃), only blood samples, AEs and concomitant medications will be collected from study patients. Concomitant medications include those used for the treatment for spasticity, depression, or fatigue and other prescription and non-prescription concomitant treatments that will be captured from the patient directly.

Patients will then receive ocrelizumab or rituximab, if they wish, as ongoing therapy. Ocrelizumab and infusion costs will be provided by Genentech until ocrelizumab is approved by the FDA and available to the patient through their insurance plan.

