For the comparator group, they may be approached to gauge interest in the study via telephone. If they are interested, the consent can be sent to them. These patients will be given the following options: 1) complete consent process orally over the phone with coordinator (and a treating physician if patient desires), sign and date the consent form and send back to coordinator via mail, fax, or email, 2) complete consent process with coordinator (and a treating physician if patient desires) in person at their next scheduled rituximab infusion. In either case, data collection will not begin until written consent is obtained. Following each rituximab infusion, nursing staff will record IRR using scales as part of standard care.

As required by the University of Colorado's Institutional Review Board, an independent Data and Safety Monitoring Board (DSMB) will meet at initiation of the study and every 6 months thereafter until the end of the study.

Table 1. Schedule of Events (for switching group)

Data Collection Event	Screening Visit^a	Day 1 (T₀) 300 mg of OCR^a	Day 15 (T₁) 300 mg of OCR)	6 months (T₂) (600 mg of OCR)	12 -18 months research termination visit (T₃)
Informed Consent	X				
Medical Exam	X				
Physical Exam	X				
Demographics and MS Disease History	X				
Concomitant Meds	X	X	X	X	X*
Vital Signs		X	X	X	X
Hepatitis B and C evaluation confirmed	X				
EDSS	X				
PDDS	X				X*
Pre-infusion blood draw:					
Lab: CBC, CMP		X		X	X
Lab: B and T cell subsets by flow cytometry		X		X	X
Lab: immunoglobulin panel		X		X	X
Lab: Binding antibodies		X		X	X
Pre and post-infusion blood draw and during moderate/severe reactions:					
Lab: Cytokine levels		X	X	X	
Administration of Ocrelizumab		X	X	X	
Pre-medication of 100 mg of methylprednisolone		X	X	X	
Nurses record IRRs		X	X	X	
Nurses/Study Coordinator record AE		X	X	X	X*
Patient self-report of IRRs		X	X	X	

* may be completed over the phone

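### The post-infusion cytokine sample is timed in two ways with no window, so draw time can track reaction grade in the comparison by grade

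*Combined protocol and SAP*

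**What the plan says.** The timing of the cytokine sample is stated in five places.

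- Introduction: "we will assay the profile of certain cytokines in the serum 4 hours after start of ocrelizumab infusion".
- Section 2.2, item b: "These blood samples will be collected before the start of each ocrelizumab infusion and following infusion completion".
- Section 3.3.2, item c: "before the start of each ocrelizumab infusion, and after the infusion is completed".
- Section 4.5.1, text: "blood samples will be collected prior to and after each infusion in CPT tubes".
- Section 4.5.1, Table 1: "Pre and post-infusion blood draw and during moderate/severe reactions".

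Only the Introduction gives a clock time. The other four refer to the infusion and give no window.

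Section 4.5.1 adds a safeguard: "Because moderate to severe infusions reactions can delay infusions, we will plan to add an additional blood draw when these reactions are detected". Its stated aims are more consistent timing and the capture of a possible peak.

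Section 3.3.2 sorts patients into Grade 0, Grades 1-2 (called mild) and Grades 3-5 (called moderate/severe), and evaluates the change in each cytokine from before to after the infusion in these groups. Section 4.9.4 plans paired t-tests of pre against post values at each infusion cycle. It has no term for sampling time.

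**The concern.** Section 2.2 wants to know whether cytokine release contributes to infusion reactions. Answering that means setting reactors against non-reactors, and the comparison is clean only if blood is drawn at the same point after start in both. A sample tied to the end of the infusion does not ensure this, because a reaction can prolong the infusion. Draw time then depends on the variable that defines the groups.

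A difference between grades could therefore partly reflect when blood was taken, and a real difference could be missed for the same reason. The Introduction links this result to whether premedication might be dropped in patients who are already depleted, so the reading matters beyond description. If draw times are not recorded, the problem cannot be adjusted for afterwards.

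**Working it through.** The plan states no figure on this point, so there is none to reproduce. The check sets the passages side by side and does the clock arithmetic.

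**1. Inputs**
- Introduction: sample at 4 h = 240 min after start.
- Section 4.3.1: "slow IV infusion over approximately 150 minutes (2.5 hours) for the 300-mg dose", so about 150 min without interruption. No length is given for 600 mg.
- Section 4.3.1: the cannula stays in for at least 60 min after the infusion.
- Section 3.3.1, Grade 2: "Requires therapy or infusion interruption but responds promptly to symptomatic treatment". Grade 3 covers reactions that do not settle quickly with medication and/or a brief interruption.

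**2. Uninterrupted 300 mg infusion**
- Gap between completion and the Introduction's time: 240 - 150 = 90 min.
- End of the minimum observation: 150 + 60 = 210 min. The 4-hour draw falls 240 - 210 = 30 min after that.

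**3. Interrupted 300 mg infusion**

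Assume an interruption of d minutes with the rate otherwise unchanged. Completion is at 150 + d. The values of d are illustrations; the documents give none.

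| d (min) | Completion (min after start) | Shift against an uninterrupted infusion (min) |
|---|---|---|
| 0 | 150 | 0 |
| 30 | 180 | 30 |
| 60 | 210 | 60 |
| 90 | 240 | 90 |

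A Grade 0 patient stays at about 150 min. A sample tied to completion therefore moves with the interruption. For d above 90 min, a draw at 4 hours would come before the infusion is finished.

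**4. Reach of the extra draw**

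It is triggered by moderate to severe reactions. In section 3.3.2 Grade 2 counts as mild, but the Introduction describes Grades 1 and 2 together as mild-to-moderate, so it is unclear whether Grade 2 triggers a draw. The pilot percentages in section 4.9.6 show how much this matters. They match 49 patients: 42/49 = 85.71% Grade 0, 6/49 = 12.24% Grade 2, and 1/49 = 2.04% Grade 3 (printed as 2.05%).
- If the trigger is Grade 3 or above: 1 of 7 reactions is covered.
- If it includes Grade 2: 7 of 7 are covered.

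The pilot is rituximab data, so carrying this mix over to ocrelizumab is an assumption.

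**5. What the extra draw leaves open**

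It is timed to the reaction, not to a set time after start. Grade 0 patients have no matching draw. The scheduled post-infusion sample still shifts. No section says whether the extra draw replaces or supplements that sample in the analysis.

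**The case against.** Several points on the other side stand.

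- A reader might infer that the two rules are 1.5 hours apart and cannot both be met. The text does not support that. Sections 2.2 and 3.3.2 ask for a sample after completion, not at the moment of completion, and for an uninterrupted 300 mg infusion a draw at 4 hours meets both wordings. The operative sections also agree with each other; the clock time appears only in the Introduction. The defect is one unreconciled sentence plus a missing window.
- A reader might treat the comparison by grade as already confounded and attach a percentage to it from an assumed cytokine half-life. That needs kinetics, an interruption length, a peak before the scheduled draw and no further release after restart, none of which is in the documents. If release continues after restart, a later sample could be higher, so even the sign is unknown.
- A reader might assume that every reaction of Grade 2 or above delays the sample. Grade 2 can mean therapy without interruption, which need not move completion.
- A reader might assume that in-reaction draws will be set against non-reactors' end samples. No section plans that. The stated analyses are of change from before to after the infusion.
- The investigators saw the timing problem and took a step against it.

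These points limit the claim but do not remove it. Section 4.5.1 accepts that reactions can delay infusions, section 3.3.2 groups by reaction grade, and nothing fixes, records or models the time of the draw.

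**Conclusion.** The concern holds as a threat built into the design, not as a measured bias. The timing statements need reconciling. As written, the time from start to the scheduled sample can differ by reaction grade. The extra draw addresses this only in part, and its trigger is ambiguous at Grade 2.

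The size of any bias cannot be given. The shift in draw time equals the length of the interruption, provided that blood is drawn at or a constant time after completion and that the rate is otherwise unchanged. What that does to a cytokine value is unknown in both size and direction.

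The outcome is listed as secondary in sections 2.2 and 3.3.2 and as exploratory in section 3.1. The primary reaction endpoint and the anti-drug antibody outcome are not affected. The change is worth making because it is cheap and cannot be made good after the samples are drawn, but the trial's main result does not depend on it.

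**What to change.** 1. Reconcile the Introduction, sections 2.2, 3.3.2 and 4.5.1, and Table 1 to one sampling time after infusion start, with a stated window for each infusion. Four hours is already in the protocol. State what applies if the infusion is unfinished at that time, and check the time against the length of the 600 mg infusion, which the documents do not give. In the same edit, settle whether cytokines are drawn at T3: section 3.3.2 lists it, Table 1 does not.
2. Record the times of infusion start, each interruption, completion, each draw and any symptomatic drug.
3. State which grades trigger the extra draw, using one meaning of moderate throughout.
4. Base the between-grade comparison on the pre-infusion and scheduled post-infusion samples, with elapsed time since start as a covariate or in a sensitivity analysis. Report in-reaction draws separately, against the same patient's own samples.

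The cost is protocol wording, a few timestamp fields and, if 4 hours is kept, a stay about 30 minutes beyond the minimum observation at the two 300 mg infusions. A fixed time is not a complete cure. After an interruption of more than 90 minutes the patient would be sampled before receiving the full dose, and symptomatic drugs may already have been given. The recorded times are needed to show where this happened.
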